The dose escalation design utilized for the present study will proceed as follows: The first subject will be enrolled at 60 Gy. Once the entire DLT window (i.e., 90 days post EBRT) is complete for this first subject, the next 2 subjects will be enrolled at 60 Gy. If in the first subject, grade 4 or higher hematuria, proctitis, fistula formation or death occurs in the DLT window, the trial will be terminated. If 2 of the first 3 subjects experience DLT at 60 Gy, the trial will be terminated. If 0 or 1 of the first 3 subjects enrolled at 60 Gy experience a DLT after the third subject's entire DLT window is complete, an additional three subjects will be enrolled at 60 Gy. If $\geq 33\%$ of subjects experience DLT at 60 Gy, the trial will be terminated. If after the sixth subject's DLT window is complete and < 33% of subjects experience DLT at 60 Gy, the first subject at 75 Gy will be enrolled. Once the entire DLT window (i.e., 90 days post EBRT) is complete for this first subject at 75 Gy, the next two subjects will be enrolled at 75 Gy. If in the first subject at 75 Gy, grade 4 or higher hematuria, fistula formation, proctitis or death occurs in the DLT window, 60 Gy will be considered the MTD and no additional subjects will be enrolled at 75 Gy. If 2 of the first 3 subjects experience DLT at 75 Gy, 60 Gy will be considered the MTD and no additional subjects will be enrolled at 75 Gy. If 1 or 0 of the first 3 subjects enrolled at 75 Gy experience a DLT after the third subject's entire DLT window is complete, an additional 3 subjects will be enrolled at 75 Gy. If $\geq 33\%$ of subjects experience DLT at 75 Gy, no additional subjects will be enrolled at 75 Gy and 60 Gy will be considered the MTD. If after the sixth subject's DLT window is complete and < 33% of subjects experience DLT at 75 Gy, 75 Gy will be considered the MTD.

The true risk of toxicity is expected to be in the range of 10-50%. The following table shows the corresponding probabilities of dose escalation.

True Risk of Toxicity	0.1	0.2	0.3	0.4	0.5
Probability of Escalation	0.96	0.87	0.69	0.50	0.31

[Type here]

Protocol Title:	A Phase I Single-Arm Open Label Dose-Escalation Study of CivaSheet with Radical Prostatectomy with or without Adjuvant External Beam Radiation Therapy in Patients with High Risk Prostate Cancer
Principal Investigator Name/Contact Info:	[name]/ [contact]/ [contact]
Primary Contact Name/Contact Info	[contact] [name]
Date Revised:	7/22/2022

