Study Number:	GCO#1: 16-1314

A minimum of 3 and a maximum of 6 subjects within a dose level must be observed for one cycle (90 day post EBRT completion) before accrual to the next higher dose level may begin.

Three patients within a dose level must be observed for one cycle (30 days post EBRT) before accrual to the next higher dose level may begin. The treatment for this study is RP + Civasheet implant + adjuvant EBRT for patients with high-risk or intermediate (non-clinically localized) prostate cancer with adverse pathologic features including seminal vesicle invasion, extra prostatic extension or a positive surgical margin. Since the clinical guidelines recommend adjuvant EBRT post RP only for patients with adverse pathologic features at RP, patients without these adverse pathologic features at RP will be replaced with additional patients at that dose level. Since however eligibility criteria is for high risk or non-clinically localized intermediate risk prostate cancer, the anticipated number of patients without these adverse pathologic features who will not receive adjuvant EBRT is 2 or less. While toxicities among these patients will be monitored according to the protocol, toxicities among these patients will not be used in determinations of the MTD. The MTD will only be determined for patients undergoing RP + Civasheet implant + adjuvant EBRT.

If a subject is withdrawn from the study prior to completing the entire cycle of therapy or prior to completing the entire DLT window without experiencing a DLT prior to withdrawal, an additional subject may be added to that dose level. Subjects missing doses due to a DLT will not be replaced since these subjects will be considered to have experienced a dose limiting toxicity.

d) Study Timelines:

The duration of an individual subject's participation in this study including follow-up is 5 years.

The expected duration for the investigators to complete this ranges between 1 month for a minimum of 1 subject and 44 months for a maximum of 12 subjects.

Table 1. Time and events table for those undergoing RP + Civasheet implant + adjuvant EBRT.

[Type here]

Effective Date: 10/18/2022

End Date: 10/17/2023

Protocol Title:	A Phase I Single-Arm Open Label Dose-Escalation Study of CivaSheet with Radical Prostatectomy with or without Adjuvant External Beam Radiation Therapy in Patients with High Risk Prostate Cancer									
Principal Investigator Name/Contact Info:	[name]/ [contact]/ [contact]									

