90 Days after Completion of EBRT

- Assessment of cumulative DLT's to decide whether progression to next dose or termination of study is necessary.

Follow-Up:

- Subjects will be followed every 6 months after completion of study treatment for 4 years or if the subject withdraws consent from participation, the subject will not be followed-up. Subjects may be followed-up by telephone or contacted by phone to schedule Mount Sinai office visits to monitor for cancer recurrence and or cancer progression in addition to late toxicity.
- Subjects will be followed yearly after completion of study treatment for 4 years or if the subject withdraws consent from participation, the subject will not be followed-up. Subjects may be followed- up by telephone or contacted by phone to schedule Mount Sinai office visits to monitor for cancer recurrence and or cancer progression in addition to late toxicity.
- If patients are not scheduled for their follow-up visits with Mount Sinai Health System, the study team will call the patient to schedule a visit.
 - If the patient schedules a follow-up at Mount Sinai, appropriate measures will be assessed according to the protocol and data will be recorded.
- If the patient is seeing a physician outside of Mount Sinai Health System, we will request that their labs and physician notes are sent to us.
 - A research coordinator will review and record the outside labs and contact the patients to collect any missing information that can be obtained by phone (i.e. bleeding, incontinence, etc.)
 - A symptomology follow-up form, as well as an IIEF assessment form are attached.
 - If additional information is necessary to assess DLTs or AEs, a coordinator will call the patient and request they schedule a follow up visit at Mount Sinai. If the patient is unable to come in for a follow-up visit, they will be dropped the study.
 - If patients are not responsive after 2 attempts, they will be considered lost to follow up and replaced.

For those with adverse pathologic features: At 1 week post RP+ Civasheet

[Type here]

Protocol Title:	A Phase I Single-Arm Open Label Dose-Escalation Study of CivaSheet with Radical Prostatectomy with or without Adjuvant External Beam Radiation Therapy in Patients with High Risk Prostate Cancer
Principal Investigator Name/Contact Info:	[name]/ [contact]/ [contact]
Primary Contact Name/Contact Info	[contact] [name]
Date Revised:	7/22/2022
Study Number:	GCO#1: 16-1314

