hematuria, proctitis, or fistula are not observed. If 2 additional subjects are enrolled at 60 Gy, we will review for DLTs after completion of the 90 day DLT window and enroll 3 additional subjects at 60 Gy if DLT has been observed in 1 subject, or enroll 1 subject at 75 Gy if no DLT were observed or terminate the trial if $\geq 33\%$ DLT were observed in all subjects. For the next group of subjects at 60 Gy, we will review DLT/toxicity after all three subjects have completed the 90 days DLT window after EBRT. After the first subject's DLT window is complete (90 days post-EBRT) at 75 Gy, we will make a decision to enroll additional subjects at 75 Gy only if Grade 4-5 hematuria, proctitis, or fistula are not observed. If 2 additional subjects are enrolled at 75 Gy, we will review for DLTs after completion of the 90 day DLT window and enroll 3 additional subjects at 75 Gy if DLT has been observed in 1 subject, or terminate the trial if $\geq 33\%$ DLT were observed among the first three subjects at 75 Gy. For the next group of three subjects at 75 Gy, we will review DLT/toxicity after all three subjects have completed the 90 days DLT window. We will additionally describe rates of complications and toxicity (i.e., acute and late overall, GU and GI) by grade and by dose once the 6 month follow-up period is complete for all subjects. Toxicities among those not receiving EBRT will not affect the MTD determination or the decision to enroll additional patients at the same dose or at a higher dose. The DMC will review data at least once annually.

If the DMC recommends termination of the study we will terminate the study. If in the first subject at any dose Grade 4-5 hematuria, proctitis or fistula occur, we will terminate the study. If $\geq 33\%$ of subjects experience DLT (i.e., Grade 3 hematuria, proctitis, urinary retention) within the first 90 days post EBRT, the trial will be closed.

The Clavien-dindo classification of surgical complications will be used to assess complications and the NCI-CTCAE v4.0 in addition to the RTOG acute and late morbidity scoring criteria will be used to grade adverse events and toxicity.

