considered the MTD. Or if the highest level (75 Gy) has been reached and < 33% of subjects have experienced DLT, 75 Gy will be considered the MTD. If in the first subject treated at 75 Gy, NCI-CTCAE Grade 4 or higher hematuria, prostatitis or fistula formation occur, no additional subjects will be enrolled at 75 Gy and 60 Gy will be considered the MTD.

**Secondary:** We will describe the adverse events, toxicity and complication profile associated with Civasheet overall and at each dose when administered with RP and EBRT and also separately for those not receiving EBRT. Overall and for 60 and 75 Gy, the toxicity and complication profile associated with the Civasheet® will be assessed. Rates for surgical complications and adverse events, acute (< 90 days) and late (18 months days) GU and GI toxicity and adverse events using the NCI-CTCAE v4.0, RTOG Acute Toxicity Scale and Late Radiation Morbidity scales will be assessed. Erectile preservation and total urinary incontinence will be assessed overall and for each dose group once all subjects have completed the 6 month follow-up after EBRT. Peri- and post-operative complications associated with surgery will be assessed and graded using the Clavien-Dindo classification of surgical complications. Erectile preservation rates [IIEF score (erectile component) > 18] will be assessed, continence defined as the use of no pads will also be assessed. Binary or categorical outcomes will be described with proportion and 95% confidence intervals and continuous measures will be summarized with mean (SD) or median (IQR), as appropriate.

BCR defined as a post-prostatectomy serum PSA > 0.2 ng/ml will also be assessed for each subject. To evaluate cancer control, the Kaplan Meier-Method will be used to estimate BCR overall and for each dose group and separately for those receiving vs. not receiving EBRT once all subjects have completed the 6 months follow-up after EBRT or 6 months follow-up after Civasheet implant if no EBRT is given.

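### Late toxicity is summarised at 6 months but carries an 18-month label in the SAP, and BCR has no first eligible PSA draw (low severity; MTD unaffected)

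*Protocol*

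**What the plan says.** **Late toxicity.** The Protocol's toxicity-review text (the block before the Adverse Events heading) undertakes to describe rates of complications and toxicity, "acute and late overall, GU and GI) by grade and by dose once the 6 month follow-up period is complete for all subjects". It does not say when the 6 months start. The SAP, under Secondary, lists "Rates for surgical complications and adverse events, acute (< 90 days) and late (18 months days) GU and GI toxicity", with no origin and no analysis time. Its nearest 6-month statement concerns erectile preservation and incontinence, which "will be assessed overall and for each dose group once all subjects have completed the 6 month follow-up after EBRT"; BCR has a similar one. The method is plain: "Binary or categorical outcomes will be described with proportion and 95% confidence intervals". The Protocol's Follow-Up text continues for 4 years "to monitor for cancer recurrence and or cancer progression in addition to late toxicity", stated once with 6-monthly visits and once with yearly visits.

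**Order of the doses.** Number of Subjects opens 75 Gy once the sixth subject's window has closed and fewer than 33% of "subjects experience DLT at 60 Gy, the first subject at 75 Gy will be enrolled". The toxicity-review text can open it after three subjects, "or enroll 1 subject at 75 Gy if no DLT were observed". Study Timelines gives "44 months for a maximum of 12 subjects".

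**BCR.** The SAP counts any PSA above 0.2 ng/ml after prostatectomy. It gives no earliest sample and no time origin. In Table 1 the lab row that bundles PSA with testosterone and BMP is marked pre-study, on Day 1, at discharge, at week 1 and at weeks 12, 23 and 35. The Follow-Up text names a 1-week clinic visit and sets PSA at each follow-up visit. The week-1 list under Procedures During Treatment does not name PSA.

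**Subjects without EBRT.** Two or fewer are expected. Table 2 marks the lab row at week 1 and then only at the routine visit, while the Follow-Up text sets PSA at each follow-up visit for them too. The SAP's Kaplan-Meier estimate for them falls due 6 months after implant.

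**The concern.** A summary made when the last subject reaches 6 months cannot deliver a late window of 18 months, whether the garbled phrase means at, up to or beyond 18 months. The toxicity-review sentence allows two tables. A fixed 6-month window per subject is fair between doses but short. A table of everything accrued by that date is longer, but unequal between doses, because 75 Gy cannot open until the 60 Gy windows have closed. The plan does not say which is meant and schedules no later table.

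For BCR, a literal reading lets PSA remaining from before surgery count as recurrence at a draw taken before EBRT starts. At stake is whether the late-toxicity and cancer-control summaries mean what their labels say, and whether windows and eligible draws are fixed before the data are seen.

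**Working it through.** **Inputs from the documents.** Surgery to start of EBRT 6 weeks (42 days); EBRT 5 weeks (35 days); DLT window 90 days; cohorts of 1, 2 and 3 subjects at each dose, each waiting for the previous window; PSA threshold 0.2 ng/ml; baseline PSA above 20 is one eligibility route. I use 30.44 days per month and 183 days for 6 months.

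**1. The plan's own figures.** Table 1's weeks reproduce: 6 + 5 + 12 = 23 and 6 + 5 + 24 = 35, so week 35 is 6 months after EBRT. One cohort takes 42 + 35 + 90 = 167 days (5.49 months). Six cohorts without gaps take 6 × 167 = 1,002 days (32.9 months) to the last DLT window, or 5 × 167 + 77 + 183 = 1,095 days (36.0 months) to the last 6-month visit. The stated 44 months would need enrolment gaps that the documents do not give. It is neither reproduced nor shown to be wrong.

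**2. If all accrued follow-up is used.** Months after EBRT at the cut = 6.0 + 5.49 × (number of later cohorts). On the six-plus-six path in Number of Subjects:

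| Cohort | 60 Gy | 75 Gy |
|---|---|---|
| 1 subject | 33.4 | 17.0 |
| 2 subjects | 28.0 | 11.5 |
| 3 subjects | 22.5 | 6.0 |
| With 18 months | 6/6 | 0/6 |

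The origin matters. Counted from implant (add 77/30.44 = 2.5 months), the first 75 Gy subject has 19.5 months and the count becomes 1/6. At the 44-month pace (44/6 = 7.33 months per cohort) that subject has 6.0 + 2 × 7.33 = 20.7 months after EBRT, again 1/6.

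If 75 Gy opens after three subjects without a DLT and also stops at three (an inference, since the toxicity-review text gives no next step there), follow-up is 22.5/17.0 against 11.5/6.0 months, and 1/3 against 0/3 reach 18 months.

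**3. If the window is fixed at 6 months.** No subject contributes 18 months. How much late toxicity is unseen depends on an assumed risk R at 18 months and on the hazard shape k: F = 1 − (1 − R)^((t/T)^k). The risk period is taken either from the end of EBRT (t = 6.01, T = 18) or from day 90 after it (t = 3.06, T = 15.04).

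- Constant hazard (k = 1), R = 20%: 1 − 0.8^(6.01/18) = 7.2% and 1 − 0.8^(3.06/15.04) = 4.4%. For R = 10% the range is 2.1–3.5%; for R = 30% it is 7.0–11.2%.
- Front-loaded hazard (Weibull, k = 0.5), R = 20%: 12.1% and 9.6%.

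So of an assumed 20 points, 4.4–7.2 appear by 6 months under one shape and 9.6–12.1 (48–60%) under the other.

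**4. Week-1 PSA.** Assume exponential decline after surgery with half-life h. From 20 to 0.2 is log2(100) = 6.64 half-lives, so a day-7 value at or below 0.2 needs h ≤ 7/6.64 = 1.05 days. The baseline above which the day-7 value exceeds 0.2 is 0.2 × 2^(7/h): 25.6 for h = 1 day, 2.3 for 2 days and 0.9 for 3.2 days. By week 12, 84/3.2 = 26 half-lives have passed even at the slowest rate, so residual pre-operative PSA no longer matters.

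**The case against.** The best defence is that little turns on this. The tables are small and descriptive, no comparison between doses is planned, and the MTD uses only the 90-day window. The exact 95% interval for 1 event in 6 is 0.4–64.1%. The Protocol sentence can also stand alone: if acute means under 90 days, events from then to 6 months are late events, and it never promises 18 months. The DMC reviews data at least annually and routine adverse events are reported annually, so late harm is not unwatched. All of this stands and sets the severity. It does not supply an origin, an analysis time for the SAP's 18-month figure, or a later table.

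Four stronger inferences go beyond the documents:

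- *The plan will make 75 Gy look safer.* This needs the all-follow-up reading. The phrase about a 6-month period fits week 35 and the SAP's other 6-month statements better, and on that reading the doses are comparable. The size also depends on how events are counted. With equal 20% risk, constant hazard and no gaps, the six-plus-six path gives about 20% against 9.3–11.2% if events are counted only to 18 months, a gap of 6 × 0.088 to 6 × 0.107, or 0.5–0.6 of one subject. With all events counted, the 60 Gy figure is 27.6–29.0%.
- *The 6-month table misses most late toxicity.* That follows under a constant hazard, but not under the front-loaded one in step 3.
- *Residual PSA is meant to count as recurrence.* No document says so. The lab row bundles three tests, and the week-1 procedure list omits PSA. The gap is that the SAP does not exclude such a value.
- *Subjects without EBRT have no PSA by 6 months.* That needs Table 2 taken alone together with the yearly schedule. The Follow-Up text and the 6-monthly statement point the other way.

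**Conclusion.** The point holds at low severity, for descriptive secondary outcomes only.

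1. The 6-month summary in the Protocol and the 18-month figure in the SAP do not fit together. On the more natural reading the doses are comparable, but 18-month toxicity cannot be shown. On the other reading, 6/6 against 0/6 subjects (or 1/6, depending on origin and pace) have 18 months on the six-plus-six path. These counts rest on document timings, no dropout and a trial that reaches 75 Gy. The share unseen at 6 months rests on assumed risks and hazard shapes and is not established.
2. The BCR rule lacks a time origin and a first eligible draw. The omission needs no assumption; its effect depends on the assumed half-life and on whether a week-1 PSA is taken.
3. The schedule for subjects without EBRT is a minor inconsistency affecting perhaps two people.

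**What to change.** **Late toxicity.** Reconcile the toxicity-review text with the SAP. State the late window and its origin: end of EBRT, or implant if no EBRT is given. At the 6-month cut, report both doses over the same per-subject window and label it toxicity to 6 months. Once all subjects have reached 18 months, report late toxicity by dose with numbers at risk, using the follow-up already planned, after the 6-monthly and yearly statements have been reconciled.

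**BCR.** In the SAP, state the time origin, exclude Day 1, discharge and week-1 values, and name the first eligible draw. On Table 1 that is week 12, one week after EBRT ends, so PSA persistence before EBRT would not be observed; the SAP should say so. State whether PSA that never falls to 0.2 or below is a Kaplan-Meier event or is reported separately.

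**Subjects without EBRT.** Reconcile Table 2 with the Follow-Up text, and do not count a subject as event-free at a time with no eligible draw.

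**Cost.** Wording in both documents plus one later table. It would come about 18 − 6 = 12 months after the 6-month cut with 6-monthly visits, or 24 − 6 = 18 months after it with yearly visits, where the first visit past 18 months is at 24.
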